### 8.2.2. Analysis of Primary Endpoint

An intention to treat analysis will be conducted of the primary outcomes for the study. Assuming that a descriptive comparison of the intervention to control group does not demonstrate statistically significant differences in terms of demographics, vaccine drivers/barriers, or vaccine knowledge, we will report on the relative rate of influenza vaccination for the intervention group compared to the control group. We will also conduct logistic regression modeling of influenza vaccination as follows:

$$logit(Y) = \beta_0 + \beta_1 M + \sum_{j} \beta_j \alpha_j + \varepsilon$$

Where:

logit(Y) = ln(Y/1-Y) for the binary variable designation of influenza vaccination status M = the binary designation for Intervention (messaging) vs Control (no messaging)  $\alpha_j =$  the baseline covariates measured in the study (e.g. demographics, vaccine drivers/barriers or knowledge)

 $\varepsilon$  = the error term of the regression.

For the logistic regression model the p-values associated with each of the  $\beta$  parameter estimates will be reported.

Version 1 17 of 22

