Participants will be sent an offer to complete a survey at baseline, 3 months, and 6 months, and a demographic and medical history survey will remain available for participants to complete throughout the study. Additional information on study experiences and intervention feedback will be gathered in the 6-month survey for those in the CVD-I group. Data from an activity tracker will be collected if one is already connected to the participant's Achievement account, consistent with their completion of the Data Usage & Permissions Agreement. Activity tracker data will be collected retrospectively and prospectively. Participants in the CVD-I arm only will be sent intervention messages on predetermined days for the duration of the 6-month study intervention period. At the end of the intervention period, individuals who completed a data usage and permissions agreement as a part of the surveys will be informed via email that the survey information they contributed was for a research study investigating influenza vaccination behavior in people with cardiovascular conditions.

Study Compliance

Evidation study staff will track whether participants are completing study-related tasks throughout the study. Participants who do not complete study activities may be contacted by email, text message, or push notifications with reminders to complete activities, within a time window that is appropriate to the specific task, but will remain in the study sample regardless of whether they submit data in a timely manner.

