7.1 Derived Data

Cardiovascular condition type will be one of the following for the purposes of the secondary analysis objectives:

- People with self-reported arrhythmia only (not including atrial fibrillation)
- People with self-reported atrial fibrillation only
- People with self-reported heart attack, cardiac arrest or coronary artery disease only
- People with self-reported congestive heart failure only
- People with self reported stroke only
- People with two or more of the above conditions
- People with other cardiovascular conditions

Vaccine drivers and barriers of interest include:

- Number of visits to a primary care provider in the 3 months prior (categorized as None, 1-2, 3 or more)
- Number of visits to a cardiology specialist in the 3 months prior (categorized as None, 1-2, 3 or more)
- Hospitalization in the 3 months prior (categorized as none, once, 2 or more)
- Offered influenza vaccination by a healthcare provider (categorized as Yes, No, Unsure)
- Healthcare provider informed individual they were in a 'high risk group' (categorized as Yes, No, Unsure)

Vaccine knowledge factors are based on responses to the survey question "What sources of information do you use to learn about the flu vaccine?", with possible responses:

- Healthcare Professionals
- Family member or peers
- Social media including blog posts
- Mobile applications
- Conventional news media (e.g. television, newspapers)

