8 STATISTICAL METHODS

8.1 General Statistical Approaches

For the study variables, we will perform distributional analysis. When describing the study population, we will use min, max, mean, and standard deviations for continuous variables (i.e. age, BMI) and frequency counts for categorical variables (i.e. gender, ethnicity). For both continuous and categorical variables, we will report on the number of participants evaluated for that variable, as well as the number of people with non-missing values. For the study variables, we will also look at individual-level rates of missing data. Missing data or unknown responses will be described separately and not be counted in the summary descriptions of the variables. We will report on the percent of missing data for each of the included data sources (surveys, activity data) and evaluate whether any missingness is associated with baseline participant-level characteristics in the case of missing survey data or with the outcome in the case of activity tracker data.

Statistical testing comparing variables will be performed at the 5% significance level using two-sided tests or two-sided 95% confidence intervals (CI), unless otherwise specified. Comparison of means will use Student's t-test for normal distributions, or a Mann-Whitney U test for non-normal distributions. Comparisons of frequencies will use chi-square tests. Regression modeling approaches are described below. We will report on the size of the beta-parameter estimate and the associated significance level (p-value) for each predictor variable.

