8.2 Analysis Population (s)

The analysis populations will consist of:

- P1: This population will consist of all individuals who respond to the 3-month or 6-month survey. It will
 be used for the primary objective analysis and for the first part of the secondary objective (examine
 predictors of vaccination status across the CVD-I and CVD-C arms). This population will also be used
 for the second exploratory objective, which is to describe self-reported complications from influenza
 during the study period.
- P2: This population will consist of all individuals who are in the CVD-I arm and have responded to the 3-month or 6-month survey. It will be used for the second part of the secondary objective, which is to describe the engagement with different intervention messages and its relationship to influenza vaccination status.
- P3a: This population will consist of individuals who responded to the baseline, 3-month or 6-month survey. It will be used to examine the first part of the exploratory objectives - specifically the selfreported impact of COVID-19 on influenza vaccination and behavior.
- P3b: This population will consist of all individuals who complete either the 3-month or the 6-month survey, who have wearable activity data and who consent in the final (6-month) survey to have the activity data analyzed for this study. This population will be used for the 3rd exploratory objective, specifically to explore the differences in wearable data (i.e., sleep, steps, heart rate) between individuals who experience influenza and those who do not, as well as differences in wearable data between cardiovascular conditions.

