8.4 Demographics and Baseline characteristics

Descriptive statistics (e.g., mean, standard deviation, frequency and percentage) of study participants will be reported for demographic variables (e.g., age, gender, education, income) and patient reported outcomes (e.g., vaccination rates). To confirm that block randomization is successful, we will compare the intervention to control groups in terms of baseline demographics, vaccine drivers/barriers, and vaccine knowledge for each of the block groups described earlier.

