8.5 Primary objective analysis

An intention to treat analysis will be conducted of the primary outcomes for the study. Assuming that a descriptive comparison of the intervention to the control group does not demonstrate statistically significant differences in terms of demographics, vaccine drivers/barriers, or vaccine knowledge, we will report on the relative rate of influenza vaccination for the intervention group compared to the control group. This is given simply by:

RR = rate of influenza vaccination among intervention group rate of influenza vaccination among control group

We will also conduct logistic regression modeling of influenza vaccination as follows:

$$logit(Y) = \beta_0 + \beta_1 M + \sum_i \beta_i \alpha_i + \varepsilon$$

Where:

logit(Y) = ln(Y/1-Y) for the binary variable designation of influenza vaccination status M = the binary designation for Intervention (messaging) vs Control (no messaging) $\alpha_j = the$ baseline covariates measured in the study (e.g. demographics, vaccine drivers/barriers or knowledge) $\epsilon = the$ error term of the regression.

Vaccine drivers and barriers are described above in Section 8.1: Derived Variables

For the logistic regression model the p-values, odds ratio and associated 95% CI associated with each of the β parameter estimates will be reported.

Kaplan-Meier curves will be constructed for time-to-influenza vaccination, using the participant estimated dates of influenza vaccination from the 3 and 6 month surveys.

- 8.6 Secondary objective analysis
- 8.6.1 To examine predictors of vaccination status, including cardiovascular condition type, vaccine drivers/barriers, and vaccine knowledge, across and between CVD-I and CVD-C.

To examine predictors of vaccination status, including cardiovascular condition type, vaccine drivers/barriers, and vaccine knowledge, across CVD-I and CVD-C we will construct the model:

$$logit(Y) = \beta_0 + \sum_i \beta_i P_i + \sum_i \beta_i \alpha_i + \varepsilon$$

Where:

logit(Y) = ln(Y/1-Y) for the binary variable designation of influenza vaccination status P_i = the predictor of interest i (e.g. cardiovascular condition, vaccine drivers/barriers, vaccine knowledge) α_j = the baseline demographics ϵ = the error term of the regression.

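### The relative vaccination rate is tied to finding no significant baseline difference; chance alone would often break that condition, and the plan does not say what then happens

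*SAP*

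**What the plan says.** SAP 8.5 calls the primary analysis intention-to-treat. It then makes a statement about baseline balance, "Assuming that a descriptive comparison of the intervention to the control group does not demonstrate statistically significant differences in terms of demographics", continues it to vaccine drivers/barriers and vaccine knowledge, and on that footing says the RR will be reported. Protocol 8.2.2 has the same condition: "Assuming that a descriptive comparison of the intervention to control group does not demonstrate statistically significant differences in terms of demographics". Neither section has a sentence for the case where the condition is not met.

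The other relevant provisions are these:

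- **Test level.** SAP 8.1: "Statistical testing comparing variables will be performed at the 5% significance level using two-sided tests". It gives t, Mann-Whitney and chi-square tests, and no multiplicity rule for baseline comparisons. The false-discovery correction in Protocol 8.2.4 is written for the exploratory outcomes.
- **Purpose of the comparison.** SAP 8.4 compares the arms on demographics, drivers/barriers and knowledge in order to confirm that block randomisation worked.
- **Source of the variables.** SAP 7.1 lists five drivers/barriers, which the SAP section 7 schedule collects by survey. On knowledge it says: "Vaccine knowledge factors are based on responses to the survey question", with five possible answers.
- **Primary population (P1).** SAP 8.2: "This population will consist of all individuals who respond to the 3-month or 6-month survey".
- **Second analysis.** A covariate-adjusted logistic model follows in SAP 8.5 without any condition. Odds ratios, 95% confidence intervals and p-values are to be reported.

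Neither document says whether the RR or the adjusted odds ratio is the primary estimate.

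**The concern.** A significance test of baseline balance is a poor criterion for deciding whether to report a treatment comparison. Among all randomised people, any difference between arms is due to chance, so a significant result does not show that randomisation failed. With many variables, such a result is common.

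Among P1 responders a difference may also reflect unequal survey response between arms. That is a real problem, but withholding the RR does not correct it.

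The primary objective is a difference in vaccination rates, and the RR is the only explicit contrast of rates between arms in the primary analysis. If its reporting depends on the balance check, the form of the headline result is settled after baseline data have been compared by arm. Because no primary estimate is named, two analysts could follow the plan and lead with different measures.

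**Working it through.** **Planning figures.** The documents give no figure for the chance of a significant baseline difference. The rates used in step 3 are the 3-point rows of the sample size table (SAP section 4; Protocol 8.1). Twice the printed arcsine formula reproduces those rows closely: 8082.0 against 8080 (35% to 38%), 8710.5 against 8710 (50% to 53%) and 8256.6 against 8256 (60% to 63%).

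**Step 1: number of tests (k).** The plan does not fix it and its lists of demographics are examples, so k is an assumption built from named items.

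- k = 10: four demographics in SAP 8.4 (age, gender, education, income), five drivers/barriers, and knowledge as one question. 4 + 5 + 1 = 10.
- k = 14: knowledge split into its five answers. 4 + 5 + 5 = 14.
- k = 16: BMI and ethnicity added from SAP 8.1. 6 + 5 + 5 = 16.

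**Step 2: chance of at least one p < 0.05 when nothing differs.** For independent tests this is 1 − 0.95^k:

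- 1 − 0.95^10 = 0.401
- 1 − 0.95^14 = 0.512
- 1 − 0.95^16 = 0.560

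For test statistics with common pairwise correlation ρ, it is 1 − ∫ φ(u) [Φ((c − √ρ·u)/√(1−ρ)) − Φ((−c − √ρ·u)/√(1−ρ))]^k du, where c is the two-sided 5% critical value. The documents give no ρ. Numerical integration gives:

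| Tests | ρ = 0 | ρ = 0.3 | ρ = 0.5 |
|---|---|---|---|
| 10 | 40.1% | 35.1% | 28.7% |
| 14 | 51.2% | 43.8% | 34.8% |
| 16 | 56.0% | 47.6% | 37.4% |

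**Step 3: what remains if the RR is not reported.** RR = p/p0 and unadjusted OR = [p/(1−p)]/[p0/(1−p0)]:

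| Planned rates | RR | Unadjusted OR |
|---|---|---|
| 35% to 38% | 0.38/0.35 = 1.086 | (0.38/0.62)/(0.35/0.65) = 1.138 |
| 50% to 53% | 0.53/0.50 = 1.060 | (0.53/0.47)/(0.50/0.50) = 1.128 |
| 60% to 63% | 0.63/0.60 = 1.050 | (0.63/0.37)/(0.60/0.40) = 1.135 |

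The planned model is adjusted, so its odds ratio need not equal these values. They show the difference in scale between the two measures.

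**Step 4: who can be checked.** Drivers/barriers and knowledge are survey answers, so for two of the three domains the check can be run only in people who answered a survey. The stated purpose in SAP 8.4 points towards everyone randomised. SAP 8.5 does not say which population governs the condition.

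**The case against.** The strongest reply is that the sentence is not a gate. It speaks of a descriptive comparison and an assumption, and contains no instruction to withhold anything. It may mean only that a crude RR is easy to interpret when the arms look alike. This reading is possible, and it is why the defect is best stated as a condition without a consequence. It does not rescue the text: the criterion is still statistical significance, and on this reading the condition can be deleted at no loss.

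A reader might infer that the primary comparison would be lost. The documents do not support that, because the adjusted logistic model is reported either way. The odds ratio and the RR also describe the same planned 3-point gain and address the same null hypothesis. What is open is the fate of the RR and which estimate leads.

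A reader might also multiply the number of tests, because SAP 8.4 plans the comparison "for each of the block groups described earlier". The available text does not define those groups or their number. Figures are missing from it, so the description may simply not be visible. No higher failure rate should be derived from that phrase.

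Nor does the plan ignore selective response. SAP 8.1 relates missing survey data to baseline characteristics, and SAP 8.3 reports response rates by arm for each survey. These provisions stand, but they do not settle what happens to the RR.

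Finally, 16 tests is a generous count: SAP 8.1 names BMI for describing the population, and SAP 8.4 does not list it among demographics.

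**Conclusion.** The point holds. Both documents attach the RR to a finding of no significant baseline difference and give no consequence if one is found. Under correct randomisation the condition would fail by chance in about 40-56% of trials with 10 to 16 independent tests, and in 29-37% at a pairwise correlation of 0.5. Both the number of tests and the correlation are assumptions; the lower range depends on that correlation, not on the test count alone. Selective response could add real differences in P1, but its size cannot be judged from the documents.

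The consequence is limited. An adjusted comparison remains whatever the balance check shows, but as an odds ratio: about 1.13-1.14 before adjustment where the RR is 1.05-1.09. Neither measure has been named primary. This should be corrected before outcomes are compared by arm; it does not invalidate the trial.

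**What to change.** In SAP 8.5 and Protocol 8.2.2:

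1. Delete the condition on baseline differences.
2. State that the RR and the risk difference, each with a 95% confidence interval, will be reported in P1 regardless of baseline balance.
3. Name in advance which of the RR and the adjusted odds ratio is the primary estimate.

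In SAP 8.4, show baseline characteristics by arm descriptively, once for everyone randomised (from profile data) and once for P1. Say that these tables inform interpretation and do not decide what is reported. Set side by side, they make differential response easier to see; they do not remove it.

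The logistic model's covariates need not change for this point. The cost is rewording in these sections and one more baseline table; no new data are needed.

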# 2. Study Objectives

#### 2.1. Primary Objective

• To determine the effectiveness of a digital intervention designed to increase influenza vaccination rates in individuals with cardiovascular diagnoses (CV diagnoses) by examining differences in self-reported influenza vaccination rates between individuals with cardiovascular disease who receive a targeted digital intervention (CVD-I) aimed at increasing influenza vaccination and those with CV diagnoses who received no intervention (CVD-C) by the end of the study period.

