3 STUDY OBJECTIVES

3.1 Primary objective

The primary endpoint in this study is to examine differences in self-reported influenza vaccination rates between individuals with cardiovascular disease who receive a targeted digital intervention (CVD-I) aimed at increasing influenza vaccination and those with cardiovascular disease who received no intervention (CVD-C).

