6 MODIFICATIONS TO THE STATISTICAL SECTION OF THE PROTOCOL

The exploratory objective, "To describe self-reported complications from influenza experienced by individuals with different cardiovascular conditions during the 6-month study period, as well as differences in complications by vaccination status" has been removed from analysis because the survey questions did not ask about specific complications of influenza.

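### Does the lack of a written rule for combining the month-3 and month-6 answers undermine the primary vaccination comparison?

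*SAP*

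**What the plan says.** Protocol 2.1 compares the intervention arm with participants "who received no intervention (CVD-C) by the end of the study period". SAP 3.1 gives the comparison with no time point: "The primary endpoint in this study is to examine differences in self-reported influenza vaccination rates".

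SAP 8.2 defines the primary population, P1, as "all individuals who respond to the 3-month or 6-month survey". Surveys are optional (Protocol 6.1), vaccination status is asked at baseline, month 3 and month 6 (SAP 7), and messages go to the intervention arm throughout the six months (SAP 5).

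SAP 8.5 then states: "we will report on the relative rate of influenza vaccination for the intervention group compared to the control group". It adds a logistic model for a yes/no vaccination status, and Kaplan-Meier curves "using the participant estimated dates of influenza vaccination from the 3 and 6 month surveys". SAP 7.1 derives condition type, drivers and barriers, and knowledge factors, but not vaccination status.

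On incomplete response, SAP 8.3 reports response to each survey by arm. SAP 8.1 will "evaluate whether any missingness is associated with baseline participant-level characteristics in the case of missing survey data".

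**The concern.** The primary outcome has no written derivation. Someone in P1 who answers no at month 3 and never answers month 6 can be coded as unvaccinated at study end, although later vaccination is possible and the messages are still running. That lowers the observed rate in both arms. If the share of such people differs by arm, the comparison can be biased in either direction. If the messages only bring forward vaccinations that would have happened anyway, the bias favours the intervention. The target effect is 3 points, so even half a point would count.

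There also seemed to be an undeclared change. SAP 3.1 lacks the protocol's time point, and the only modification listed in SAP 6 is an exploratory objective that "has been removed from analysis because the survey questions did not ask about specific complications of influenza".

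**Working it through.** **Was the time point dropped?** No. SAP 3.1 repeats Protocol 4.1, which has no time point either, and the undated outcome in SAP 8.5 comes from Protocol 8.2.2. SAP 6 therefore had nothing to list, and the cut-off in Protocol 2.1 still stands.

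**The plan's own figures.** For 50% against 53%, the arcsine formula with two-sided alpha 0.05 and power 0.80 gives 4,355 per arm. Doubled, this is 8,711, against 8,710 in the table. SAP section 4 expects 49,000 × 0.16 = 7,840 respondents, or 3,920 per arm, so the standard error of the difference near 50% is √(2 × 0.25/3,920) = 0.01129 (1.13 points).

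**Equal arms.** Let s be the month-3-only share of P1 and f the share of final vaccinations that come after the month-3 answer. The observed rate is the true rate × (1 − s·f). With equal s and f, RR = 0.53(1 − s·f) / [0.50(1 − s·f)] = 1.06, which is unbiased. For s of 10–40% and f of 5–30% (assumed), the difference falls from 3.0 to between 2.98 and 2.64 points. Power at N = 8,000 falls from 76.6% to between 76.1% and 66.0%.

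**Unequal arms.** All inputs here are assumptions. Let u be the rise in points between month 3 and month 6 among month-6 respondents, and k the later uptake of month-3-only respondents relative to theirs. With equal month-3 rates, the error in one arm is:

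- crude rate: −s·k·u
- Kaplan-Meier, censoring at the last answered survey: +s·(1 − k)·u
- month-6 respondents only: +s·(1 − k)·u

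Case A: the month-3-only shares differ by g, so the crude bias has size k·u·g. Case B: shares are equal and messages bring d points forward, so the bias is +s·k·d.

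| Case | k = 0.25 | k = 0.5 | k = 1 |
|---|---|---|---|
| A, u = 5, g = 2 points | 0.025 | 0.05 | 0.10 |
| A, u = 10, g = 10 points | 0.25 | 0.5 | 1.0 |
| B, s = 10%, d = 2 | 0.05 | 0.1 | 0.2 |
| B, s = 40%, d = 4 | 0.4 | 0.8 | 1.6 |

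If the true difference is zero, the rejection probability is Φ(b/SE − 1.96) + Φ(−b/SE − 1.96). It is 5.1% for a bias b of 0.1 point, 7.3% for 0.5, 10.9% for 0.8, 14.4% for 1.0 and 29.4% for 1.6.

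**Would other estimates be better?** Take shares of 30% (intervention) and 20% (control) with u = 8, so s·u differs by 0.8 points. The crude bias is −0.8k and the Kaplan-Meier bias +0.8(1 − k):

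| k | Crude | Kaplan-Meier |
|---|---|---|
| 0.25 | −0.20 | +0.60 |
| 0.5 | −0.40 | +0.40 |
| 1 | −0.80 | 0.00 |

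A simulation of 4,000 runs agrees. Kaplan-Meier is less biased only if k exceeds 0.5, and the documents say nothing about k.

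Now let k differ by arm, with s = 20% and u = 8 in both (s·u = 1.6 points), k = 0.25 in the intervention arm and k = 1 in control:

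- crude: −0.4 − (−1.6) = +1.2 points
- Kaplan-Meier: 1.6 × 0.75 − 0 = +1.2 points
- month-6 respondents only: +1.2 points

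All three agree, and all are wrong. In the simulations the standard deviation of the difference was 1.12–1.14 points (crude), 1.17–1.19 (Kaplan-Meier) and 1.26–1.32 (month-6 respondents only), so the alternatives also cost precision.

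**The case for a change.** The strongest case for a change is that this is the primary endpoint and several codings fit the text: yes at either survey, the latest answer, or month 6 alone. The choice could be made after the data are seen. Only one arm receives messages, and these include reminders and scheduling tasks, so a difference in month-6 response or in vaccination timing is plausible. The assumed ranges can also be widened. With u = 15 and k = 1, a gap of 10 points in month-3-only share gives a false difference of 1.5 points, and a gap of 20 points gives 3.0, as large as the target. One sentence in the SAP would cost almost nothing.

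Part of this stands. The derivation is unwritten, and the planned curves have no stated censoring rule. Baseline yes, conflicting and unsure answers have no stated coding either. But the objective and the population together point to one coding. A 10- or 20-point gap between arms would show in the response counts that SAP 8.3 already requires. The large biases come from people not answering month 6, and writing the natural rule down would not reduce them. An extra estimate helps only under values of k that nobody can check from these documents. A rule that calls the result robust when the estimates agree could reassure falsely, as the 1.2-point example shows.

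**Conclusion.** This is missing detail that analysts can fill sensibly. No change to the plan follows. The end-of-study cut-off is in Protocol 2.1, P1 admits a response at either survey, and a yes at either survey is the natural reading. The planned crude comparison would be kept under any of the remedies considered.

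The documents do not allow the bias to be sized. It is zero for the relative rate when the month-3-only share, its relative later uptake and the ratio of month-3 to month-6 rates are equal in both arms. In the tabulated cases it is 0.03–1.6 points (0.05–0.8 at k = 0.5). The top value needs k = 1, a 40% month-3-only share and 4 points merely brought forward, which is more than the whole planned effect. Nothing shows that following the plan gives a wrong answer, or that an added estimate would be closer to the truth.

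This rests on the month-6 question covering the whole season, which cannot be checked because the questionnaires are not in the documents, and on similar month-3 rates in those who did and did not go on to answer month 6.
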